Clinical Study Protocol

Drug Substance ZD9393
Study Code D8666C00001
Edition Number 1

An Open Label, Randomised, Parallel Group, Multicentre Study to Compare ZOLADEX™ 10.8 mg Given Every 12 Weeks with ZOLADEX 3.6 mg Given Every 4 Weeks in Pre-menopausal Women with Oestrogen Receptor Positive Advanced Breast Cancer

Sponsor:

The following Amendment(s) and Administrative Changes have been made to this protocol since the date of preparation:

Amendment No.	Date of Amendment	Local Amendment No:	Date of Local Amendment
_____	_____	_____	_____
_____	_____	_____	_____
_____	_____	_____	_____
Administrative Change No.	Date of Administrative Change	Local Administrative Change No.	Date of Local Administrative Change
_____	_____	_____	_____
_____	_____	_____	_____
_____	_____	_____	_____

This submission /document contains trade secrets and confidential commercial information, disclosure of which is prohibited without providing advance notice to AstraZeneca and opportunity to object.

PROTOCOL SYNOPSIS

An Open Label, Randomised, Parallel Group, Multicentre Study to Compare ZOLADEX™ 10.8 mg Given Every 12 Weeks with ZOLADEX 3.6 mg Given Every 4 Weeks in Pre-menopausal Women with Oestrogen Receptor Positive Advanced Breast Cancer

International Co-ordinating Investigator

Principal Investigators

Study centre(s) and number of subjects planned

This study will be conducted in approximately 216 randomised patients in Asian countries. The planned countries to be included in this study are: China, Thailand, India, Japan, Korea, and Philippines etc..

Study period

Phase of development

Estimated date of first subject enrolled

III

Estimated date of last subject completed

The end of study is defined as the last visit of the last patient undergoing the study.

Objectives

The primary objective of this study is to evaluate whether ZOLADEX 10.8 mg is non-inferior to ZOLADEX 3.6 mg in pre-menopausal women with oestrogen receptor (ER) positive advanced breast cancer by assessment of progression-free survival (PFS) at 24 weeks.

The secondary objectives are:

- To provide supportive data confirming that ZOLADEX 10.8 mg is non-inferior to ZOLADEX 3.6 mg by assessment of:

- Objective response rate (ORR) at 24 weeks, determined by Response Evaluation Criteria In Solid Tumours (RECIST) criteria (Ver.1.1)
- Oestradiol (E₂) serum concentrations at 24 weeks
- To compare the safety and tolerability profile of ZOLADEX 10.8 mg and ZOLADEX 3.6 mg by assessment of adverse events (AEs)
- To assess the pharmacokinetics of goserelin in Japanese and Non Japanese patients except for patients in China in the PK sub-group following administration of ZOLADEX 10.8 mg by measurement of plasma concentrations of goserelin. And to assess the E₂ serum concentration profiles in the PK sub-group.

Study design

This is a multicentre, open label, randomised, parallel group study to compare ZOLADEX 10.8 mg given every 12 weeks with ZOLADEX 3.6 mg given every 4 weeks.

Target subject population

Pre-menopausal female patients with locally advanced or metastatic ER positive breast cancer who are candidates to receive hormonal therapy.

Investigational product (ZOLADEX 10.8 mg)

- ZOLADEX 10.8 mg (goserelin acetate): one subcutaneous depot injection once every 12 weeks (\pm 7 days).
- One oral tamoxifen 20 mg tablet daily.

Comparator (ZOLADEX 3.6 mg), dosage and mode of administration

- ZOLADEX 3.6 mg (goserelin acetate): one subcutaneous depot injection once every 4 weeks (\pm 7 days).
- One oral tamoxifen 20 mg tablet daily.

Duration of treatment

Study medication will be administered from Day 1 until completion of 24 weeks of study treatment or any other criterion for treatment discontinuation are met whichever is sooner.

Outcome variables

Primary outcome variable

- Efficacy

- The primary outcome variable is PFS at 24 weeks. A progression-free patient is defined as a patient for whom neither objective disease progression nor death (due to any cause) has been observed

Secondary outcome variables

- Efficacy/PD
 - ORR at 24 weeks: with response defined as either a complete or partial response based on the RECIST criteria (Ver. 1.1)
 - E₂ serum concentrations at 24 weeks
 - E₂ serum concentration profiles (PK sub-group only)
- Safety
 - AE profile
- PK analysis
 - Plasma concentration–time profile and related PK parameters of goserelin

Statistical methods

The non-inferiority of ZOLADEX 10.8 mg to ZOLADEX 3.6 mg will be tested using 95% confidence intervals (CI) of the difference (ZOLADEX 10.8 mg – ZOLADEX 3.6 mg) of proportions of patients with progression-free at 24 weeks. The non-inferiority will be concluded when the lower limit of the CI is greater than or equal to –17.5%. The choice of this limit is based on a 75% relative efficacy of ZOLADEX 10.8 mg to ZOLADEX 3.6 mg, for which a 24-week progression-free proportion of 70% is anticipated.

Assuming the proportion of patients who are progression-free at 24 weeks is 70% in both treatment groups in this study, and define the limit of non-inferiority as an absolute difference of 17.5% between these two proportions, a sample size of 216 patients (108 per group) ensures that 80% power is achieved to conclude non-inferiority with a two-sided 95% CI.

	PAGE
TITLE PAGE	1
PROTOCOL SYNOPSIS.....	2
TABLE OF CONTENTS.....	5
LIST OF ABBREVIATIONS AND DEFINITION OF TERMS	10
1. INTRODUCTION	13
1.1 Background	13
1.2 Research hypothesis.....	14
1.3 Rationale for conducting this study	14
1.4 Benefit/risk and ethical assessment.....	15
2. STUDY OBJECTIVES.....	15
2.1 Primary objective	15
2.2 Secondary objectives	15
2.3 Safety objective.....	16
2.4 Exploratory objectives - NA	16
3. STUDY PLAN AND PROCEDURES	16
3.1 Overall study design and flow chart	16
3.1.1 PK subgroup and schedule.....	17
3.2 Rationale for study design, doses and control groups.....	23
4. SUBJECT SELECTION CRITERIA	23
4.1 Inclusion criteria	23
4.2 Exclusion criteria	24
5. STUDY CONDUCT	25
5.1 Restrictions during the study	25
5.2 Subject enrolment and randomisation.....	26
5.2.1 Procedures for randomisation	26
5.2.2 Assignment to the pharmacokinetic subgroup	27
5.3 Procedures for handling subjects incorrectly enrolled or randomised.....	27
5.4 Blinding and procedures for unblinding the study - NA.....	27
5.5 Treatments.....	27

5.5.1	Identity of investigational product(s).....	27
5.5.2	Doses and treatment regimens	28
5.5.2.1	Treatment procedure of study medication	28
5.5.3	Labelling	29
5.5.4	Storage	30
5.6	Concomitant and post-study treatment(s)	30
5.6.1	Pre-study medications	30
5.6.2	Concomitant medications.....	30
5.6.3	Medication after discontinuation of study drug	30
5.7	Treatment compliance.....	30
5.7.1	Accountability.....	31
5.8	Discontinuation of study treatment	32
5.8.1	Procedures for discontinuation of a subject from investigational product	33
5.9	Withdrawal from study	33

AST	Aspartate aminotransferase (serum glutamic pyruvic transaminase [SGPT])
AUC	Area under the curve
AUC _(0-t)	Area under the curve - time curve from 0 to time t
AUC _(0-12 weeks)	Area under the curve- time curve from 0 to Week 12
CI	Confidence interval
C _{max}	Maximum plasma concentration
conc.	Concentration
CPD	AstraZeneca Clinical Pharmacology & DMPK (CPD)
CSA	Clinical Study Agreement
CSR	Clinical Study Report
CT	Computerized Tomography
CTCAE v3.0	Common Terminology Criteria for Adverse Events v3.0
DAE	Discontinuation of Investigational Product due to Adverse Event
D/d	Day or day
DMPK	Drug Metabolism and Pharmacokinetics
EC	Ethics Committee, synonymous to Institutional Review Board (IRB) and Independent Ethics Committee (IEC)
eCRF	electronic Case Report Form
ER	Oestrogen receptor
E ₂	Oestradiol
FAS	Full analysis set
FSH	Follicle stimulating hormone
GCP	Good Clinical Practice
GMP	Good Manufacturing Practice
GnRH(a)	Gonadotrophin-releasing hormone (analogue)

Abbreviation or special term	Explanation
h	hour
HER2	Human Epidermal Growth Factor Receptor 2
HRT	Hormone replacement therapy
IB	Investigators Brochure
ICF	Informed consent form
ICH	International Conference on Harmonisation
IP	Investigational Product
IRB	Institutional Review Board
IWRS	Interactive Web Response System
LH	Luteinising hormone
LHRH(a)	Luteinising hormone-releasing hormone (analogue)
LLOQ	Lower Limit of Quantification
LSLV	Last Subject Last Visit
max	maximum
MedDRA	Medical Dictionary for Regulatory Activities
MHLW	Ministry of Health, Labour and Welfare
min	minimum
MRI	Magnetic resonance imaging
NE	Not Evaluable
NCI	National Cancer Institute
OAE	Other Significant Adverse Event (see definition in Section 11.2.1)
ORR	Objective Response Rate
PD	Progression Disease
PFS	Progression Free Survival
PgR	Progesterone Receptor
PI	Principal Investigator
PK	Pharmacokinetic
PPS	Per protocol set
RECIST	Response Evaluation Criteria In Solid Tumours
SAE	Serious Adverse Event (see definition in Section 6.4.2).
SAP	Statistical Analysis plan
SD	Standard Deviation

Abbreviation or special term	Explanation
SDV	Source Data Verification
T _{max}	Time to maximum plasma concentration
TNM	Tumour, node, metastases
ULRR	Upper limit of Reference Range
WBDC	Web Based Data Capture
WHO	World Health Organization
Wk	Week
International Co-ordinating investigator	If a study is conducted in several countries the International Co-ordinating Investigator is the Investigator co-ordinating the investigators and/or activities internationally.
Investigator(s)	Principal investigator and sub investigator

1. INTRODUCTION

Breast cancer is the most common cancer in women, and is second only to lung cancer as a cause of cancer death in women (Dumitrescu et al 2005). Approximately 10% of newly diagnosed patients have locally advanced or metastatic disease, and approximately 20% to 85% of patients who are diagnosed with early breast cancer will later develop recurrent and/or metastatic disease (Bernard-Marty et al 2004). The median survival time after diagnosis of metastasis is approximately 2 years (Bernard-Marty et al 2004).

17 β -Oestradiol (E₂) has a growth-promoting role in the pathogenesis of E₂-dependent breast cancer (Klijn et al 2000). Disease management strategies therefore include E₂ deprivation/antagonism by either medical or surgical means (Klijn et al 2000). In pre-menopausal women, the ovaries are the primary source of oestrogen and surgical ovarian ablation is the traditional option (Klijn et al 2000). However, oophorectomy is irreversible. An alternative is the use of reversible endocrine therapies such as gonadotrophin-releasing hormone/luteinising hormone-releasing hormone analogues (GnRHa/LHRHa).

AstraZeneca ZD9393 (goserelin acetate, ZOLADEX^{TM1}) is a synthetic GnRHa. GnRH stimulates the release of luteinising hormone (LH) and follicle stimulating hormone (FSH), which in pre-menopausal women regulate the cyclical synthesis and release of oestrogen and progesterone from the ovaries. On chronic administration in women, goserelin causes potentially reversible ovarian ablation resulting in oestrogen suppression and amenorrhoea in the majority of patients, rendering the patient menopausal.

Relevant pre-clinical data for ZOLADEX 10.8 mg and ZOLADEX 3.6 mg are presented in the latest Investigator's Brochure (IB).

1.1 Background

The efficacy, safety and endocrine effects of ZOLADEX 3.6 mg, administered every 4 weeks, in pre- and peri-menopausal women with advanced breast cancer are well documented (Dalton et al 1987, Boccardo et al 1994, Jonat et al 1995, Taylor et al 1998; see the latest ZOLADEX IB), and ZOLADEX 3.6 mg is approved in this indication in many countries.

ZOLADEX 10.8 mg given every 12 weeks is approved in many countries for use in prostate cancer, endometriosis and uterine fibroids and has been shown to be as effective as 4-weekly injections of ZOLADEX 3.6 mg in the management of prostate cancer in patients of both European and Japanese origin (studies 118630/1805, 9393HQ/0001, and ZD-55-11, see the latest ZOLADEX IB). This formulation is potentially more convenient than ZOLADEX 3.6 mg due to its less frequent administration.

¹ ZOLADEX is a trademark of the AstraZeneca group of companies.

ZOLADEX 10.8 mg was investigated in 1991 in an open, uncontrolled study of 21 pre- and peri-menopausal women with advanced breast cancer (study 9393HQ/0002, see the latest ZOLADEX IB). E₂ suppression was measured as a marker of clinical efficacy and successful E₂ suppression was defined as all on-dose E₂ measurements less than 92 pmol/L. The E₂ suppression was assessed in the total 19 patients, and there were 9 patients (47 %) of failures seen in this study, but in the majority of cases failure was due to a transient increase of E₂ levels above the 92 pmol/L threshold and there was no consistent time of failure. Further investigation showed that there was no consistent relationship between the transient increase in E₂ level and clinical outcome in these patients: 1 patient with a partial objective tumour response had a transient increase in E₂ while 3 patients had disease progression but their E₂ levels were consistently below the post-menopausal threshold. When the threshold was revised to 140 pmol/L, in line with results published in 1995, E₂ suppression was successfully maintained for up to 84 days (3 menstrual cycles) after administration of ZOLADEX 10.8 mg in 15 of 17 evaluable patients receiving the first depot and 12 out of 13 patients receiving the second depot.

Initial 12-week data in female patients with endometriosis indicated that ZOLADEX 10.8 mg was less effective in suppressing E₂ than ZOLADEX 3.6 mg, although the differences between the products were relatively small and of uncertain clinical relevance (study 9393IL/0026, see the latest ZOLADEX IB). However, longer follow-up data in women with benign gynaecological conditions indicated that, after 24 weeks of therapy, the differences between ZOLADEX 10.8 mg and ZOLADEX 3.6 mg are very small in terms of E₂ suppression (6% difference in E₂ area under the plasma concentration–time curve over a 24-week period) with no difference in clinical outcomes over a 24 to 96 weeks (6 to 24 months) period (studies 9393IL/0026 and 9393IL/0027, data on file).

In Japan, trial 0004 was started in 2005 to compare the effect in suppressing E₂ between ZOLADEX 10.8 mg and ZOLADEX 3.6 mg in adjuvant therapy and the result showed ZOLADEX 10.8 mg was non-inferior to ZOLADEX 3.6 mg in terms of E₂ suppression in pre-menopausal patients with ER positive breast cancer. Furthermore, in east Europe and Japan, international trial (trial 0008) was started in 2006 to verify the non-inferiority of ZOLADEX 10.8 mg to ZOLADEX 3.6 mg in pre-menopausal patients with locally advanced or metastatic breast cancer but the recruitment was halted in December 2007 due to lower rate of recruitment in east Europe than expectation.

1.2 Research hypothesis

The primary objective of this study is to evaluate whether ZOLADEX 10.8 mg is non-inferior to ZOLADEX 3.6 mg in pre-menopausal women with ER positive advanced breast cancer by assessment of PFS at 24 weeks.

1.3 Rationale for conducting this study

As described in Section 1.1, as a result of trial 0004, ZOLADEX 10.8 mg was non-inferior to ZOLADEX 3.6 mg in terms of E₂ suppression in pre-menopausal patients with ER positive breast cancer. On the other hand, trial 0008 conducted in east Europe and Japan was halted

due to poor recruitment. However, the data of 98 patients who were randomised until December 2007 was analysed and the result showed that PFS at week 24 was around 70% in ZOLADEX 10.8 mg and in ZOLADEX 3.6 mg and the efficacy of ZOLADEX 10.8 mg seemed to be similar to that of ZOLADEX 3.6 mg. There were no issue of efficacy and safety, which required to discontinue the trial as of data cut off in June 2008.

Therefore it was considered to be possible to verify the non-inferiority of ZOLADEX 10.8 mg to ZOLADEX 3.6 mg statistically, by conducting and completing a similar study to the trial 0008. ZOLADEX 10.8 mg could offer a more convenient therapy to patients with breast cancer than ZOLADEX 3.6 mg due to its less frequent administration schedule. This study will be conducted in Asia including Japan.

This study will be conducted in compliance with the protocol, International Conference on Harmonisation (ICH) Good Clinical Practice (GCP) and applicable regulatory requirements.

1.4 Benefit/risk and ethical assessment

In women, ZOLADEX suppresses serum E₂ concentrations, which for 4-weekly ZOLADEX 3.6 mg administration is associated with a response in hormone-dependent breast cancer. The 12-weekly ZOLADEX 10.8 mg offers a potentially more convenient (less frequent) therapy to patients with breast cancer. Current data indicate little clinical difference of serum E₂ suppression between the 2 formulations in pre-menopausal breast cancer in trial 0004.

Generally, ZOLADEX 3.6 mg is well-tolerated in patients with breast cancer with the most frequent AEs being those commonly associated with serum E₂ suppression. Initially, breast cancer patients given ZOLADEX 3.6 mg may experience a temporary increase of serum E₂, signs and symptoms, which can be managed symptomatically. The most frequent AEs caused by ZOLADEX 10.8 mg is commonly associated with serum E₂ suppression and they can be managed symptomatically .

This study has a favourable risk/benefit assessment.

2. STUDY OBJECTIVES

2.1 Primary objective

The primary objective of this study is to evaluate whether ZOLADEX 10.8 mg is non-inferior to ZOLADEX 3.6 mg in pre-menopausal women with oestrogen receptor (ER) positive advanced breast cancer by assessment of progression-free survival (PFS) at 24 weeks.

2.2 Secondary objectives

The secondary objectives are

- To provide supportive data confirming that ZOLADEX 10.8 mg is non-inferior to ZOLADEX 3.6 mg by assessment of:

- Objective response rate (ORR) at 24 weeks, determined by Response Evaluation Criteria In Solid Tumours (RECIST) criteria (Ver.1.1)
- Oestradiol (E₂) serum concentrations at 24 weeks
- To compare the safety and tolerability profile of ZOLADEX 10.8 mg and ZOLADEX 3.6 mg by assessment of adverse events (AEs)
- To assess the pharmacokinetics of goserelin in Japanese and Non Japanese patients except for patients in China in the PK sub-group following administration of ZOLADEX 10.8 mg by measurement of plasma concentrations of goserelin. And to assess the E₂ serum concentration profiles in the PK sub-group.

2.3 Safety objective

See Section 2.2

2.4 Exploratory objectives - NA

3. STUDY PLAN AND PROCEDURES

This Clinical Study Protocol has been subject to a peer review according to AstraZeneca standard procedures.

3.1 Overall study design and flow chart

This is a multicentre, open label, randomised, parallel group study to compare ZOLADEX 10.8 mg given every 12 weeks with ZOLADEX 3.6 mg given every 4 weeks.

Target subject population

Pre-menopausal female patients with locally advanced or metastatic ER positive breast cancer. (See Section 4.1 and 4.2 for inclusion and exclusion criteria)

Study medication

‘Study medication’ is a combination of investigational product ‘ZOLADEX 10.8 mg’ or comparator ‘ZOLADEX 3.6 mg’ and study concomitant medication ‘tamoxifen’.

Study period

This study period is composed of screening period and study treatment /assessment period.

Screening period (Visit 1, Day – 21 to Day 0)

- Only eligible patients should be randomised by assessment based on the inclusion criteria and exclusion criteria (See Section 4.1 and 4.2).

- Eligible patients will be randomised 1:1 to receive ZOLADEX 10.8 mg or ZOLADEX 3.6 mg at visit 2.

Treatment/Assessment period

Administration of Investigational product (ZOLADEX 10.8 mg) or comparator (ZOLADEX 3.6 mg) should be started within 1 day after randomisation. Study concomitant medication (Tamoxifen 20 mg) should be started on the same day of or one day after starting the administration of ZOLADEX.

Study medication will be administered from Day 1 until completion of 24 weeks of study treatment or any other criterion for treatment discontinuation are met whichever is sooner. In other words, administration of ZOLADEX 10.8 mg will be continued until Week 12 or any other criterion for treatment discontinuation are met whichever is sooner. Administration of ZOLADEX 3.6 mg will be continued until Week 20 or any other criterion for treatment discontinuation are met whichever is sooner. Administration of tamoxifen will be continued until Week 24 or any other criterion for treatment discontinuation are met whichever is sooner.

Assessment schedule

Study visits to assess efficacy and safety are scheduled at Day 1 (Visit 2), Week 12 (Visit 3), and Week 24 (see Table 2 for study visit windows).

Assessments to identify disease progression will be conducted at each scheduled visit, Week 12 and Week 24. Assessments for progressive disease will also be done between scheduled visits as clinically indicated.

Final assessment of efficacy will be done at the time of disease progression or at Week 24 (Study completion visit) whichever is sooner.

Final assessment of safety will be done at Week 24 (Study completion visit) but if criterion for treatment discontinuation is met before Week 24, the assessment will be done 12 weeks after the final administration of ZOLADEX 10.8 mg or 4 weeks after the final administration of ZOLADEX 3.6 mg respectively or at Week 24 whichever is sooner.

The principal investigator/sub-investigator is responsible for following the schedule of study procedures as defined in the study protocol.

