5.5.2 Doses and treatment regimens

5.5.2.1 Treatment procedure of study medication

During the treatment period, patients will receive either ZOLADEX 3.6 mg or ZOLADEX 10.8 mg at dose visits:

Patients will be administered ZOLADEX at the study centre by the investigator(s) (or by designated medically qualified or nursing study centre personnel if local regulatory guidelines permits. It is highly recommended that patients attend the study centre for all dose visits. When dosing at the study centre is not possible, medically qualified or nursing study centre personnel may visit the patients for home study drug administration.

Arm of patients who will take Investigational product (ZOLADEX 10.8 mg)

- ZOLADEX 10.8 mg (goserelin acetate): one subcutaneous depot injection into interior abdominal wall once every 12 weeks (\pm 7 days). (i.e. Visit 2, Visit 3)

- One oral tamoxifen 20 mg tablet daily.

Arm of patients who will take Comparator (ZOLADEX 3.6 mg)

- ZOLADEX 3.6 mg (goserelin acetate): one subcutaneous depot injection into interior abdominal wall once every 4 weeks (± 7 days)(i.e. Visit 2, Week 4, Week 8, Week 12:Visit 3, Week 16 and Week 20)
- One oral tamoxifen 20 mg tablet daily.

<<Japan Specific procedures>>

In Japan, the patients must visit the study centre and the patients will be administered ZOLADEX 3.6 mg or ZOLADEX 10.8 mg by investigator(s). (Ditto with Section 5.7 in the clinical study protocol).

The following contents in Section 5.5.2.1 of the clinical study protocol do not apply to the Japanese study.

“When dosing at the study centre is not possible, medically qualified or nursing study centre personnel may visit the patients for home study drug administration.”

Patients will be given pack of tamoxifen containing sufficient tablets for 24 weeks supply at Visit2.

Patients will administer tamoxifen by themselves and will be instructed as follows:

- To swallow the tablet whole with water or another non-alcoholic drink at approximately the same time each day.
- In the case that a dose is missed, to take the missed tablet as soon as they remember and to take the next dose as scheduled, unless it is almost time for their next dose, or they remember at the next dose.
- To return a bottle of tamoxifen.

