The Investigator will assess causal relationship between Investigational Product and each Adverse Event, and answer “yes” or “no” to the question “Do you consider that there is a reasonable possibility that the event may have been caused by the investigational product?”

For SAEs causal relationship will also be assessed for other medication and study procedures and additional study drug. Note that for SAEs that could be associated with any study procedure the causal relationship is implied as “yes”.

A guide to the interpretation of the causality question is found in Appendix B to the Clinical Study Protocol.

Adverse Events based on signs and symptoms

All AEs spontaneously reported by the subject or reported in response to the open question from the study personnel: “*Have you had any health problems since the previous visit/you were last asked?*”, or revealed by observation will be collected and recorded in the eCRF. When collecting AEs, the recording of diagnoses is preferred (when possible) to recording a list of signs and symptoms. However, if a diagnosis is known and there are other signs or symptoms that are not generally part of the diagnosis, the diagnosis and each sign or symptom will be recorded separately.

Adverse Events based on examinations and tests

The results from protocol mandated laboratory tests and vital signs will be summarised in the clinical study report. Deterioration as compared to baseline in protocol-mandated laboratory values should therefore only be reported as AEs if they fulfil any of the SAE criteria or are the reason for discontinuation of treatment with the investigational product.

If deterioration in a laboratory value/vital sign is associated with clinical signs and symptoms, the sign or symptom will be reported as an AE and the associated laboratory result/vital sign will be considered as additional information. Wherever possible the reporting investigator(s) uses the clinical, rather than the laboratory term (eg, anaemia versus low haemoglobin value). In the absence of clinical signs or symptoms, clinically relevant deteriorations in non-mandated parameters should be reported as AE(s).

Deterioration of a laboratory value, which is unequivocally due to disease progression, should not be reported as an AE/SAE.

Any new or aggravated clinically relevant abnormal medical finding at a physical examination as compared with the baseline assessment will be reported as an AE.

Disease progression

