12.2.2 Analysis of safety outcome variables (main study)

12.2.2.1 Adverse events

AEs will be classified by MedDRA preferred term (PT) and system organ class (SOC).

All data on AEs that occurred after obtaining informed consent will be listed. AEs that occurred after administration of the investigational product will be summarised by treatment group, SOC, PT and the worst Grade of CTCAE v3.0. Drug related adverse events data will also be summarised in the same manner.

Individual patient data on all SAEs, deaths and AEs leading to discontinuation of the study as well as all AEs assessed, as OAEs will be listed.

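### Six planned post-dose staff contacts on 3.6 mg against two on 10.8 mg leave the by-arm all-AE incidence open to under-recording of mild, transient events on 10.8 mg

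*Protocol*

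**What the plan says.** Section 3.1 sets one safety schedule for both arms: "Study visits to assess efficacy and safety are scheduled at Day 1 (Visit 2), Week 12 (Visit 3), and Week 24".

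Section 5.5.2.1 sets different injection contacts. The 3.6 mg arm is dosed at "Visit 2, Week 4, Week 8, Week 12:Visit 3, Week 16 and Week 20"; the 10.8 mg arm is dosed at two visits only ("i.e. Visit 2, Visit 3"). These contacts are in person: "It is highly recommended that patients attend the study centre for all dose visits", with home administration by study personnel as the fallback outside Japan. Section 3.1.1 gives the PK subgroup (at least 20 patients, all on 10.8 mg) further sampling visits at Day 2, Day 3 and Week 4.

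Section 6.4.3 sets out how AEs are captured: "All AEs spontaneously reported by the subject or reported in response to the open question from the study personnel", plus anything revealed by observation. The question is "Have you had any health problems since the previous visit/you were last asked". None of the three routes is confined to the common visits.

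Comparing the safety and tolerability of the two regimens through AEs is a secondary objective (Section 2.2). The planned output is in Section 12.2.2.1: "AEs that occurred after administration of the investigational product will be summarised by treatment group", by system organ class, preferred term and worst CTCAE grade. SAEs, deaths and AEs leading to discontinuation are to be listed by patient. Section 12.2 confines formal testing to efficacy and PD.

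**The concern.** Between Day 1 and Week 24, a 3.6 mg patient has four planned meetings with study staff that a 10.8 mg patient outside the PK subgroup does not have. Whatever she mentions or staff notice at those meetings has to be recorded. If the open question is asked there too, she looks back over about 4 weeks, and the 10.8 mg patient over about 12.

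Serious, severe or lasting events should come to light under either schedule. Mild events that start and resolve between visits are the ones at risk. Section 6.4.3 adds weight to symptoms: deteriorations in protocol-mandated laboratory values count as AEs only if serious or the reason for stopping treatment, so the non-serious AE count rests mainly on what patients report.

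The by-arm AE summaries are the main evidence for the comparative safety objective. The trial is open label, and Section 3.2 defends that choice only for PFS, as an objectively assessed outcome. A shortfall in recording on 10.8 mg would read as better tolerability.

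**Working it through.** **The protocol's own figures.** It states no AE incidence, recall loss or contact ratio, so there is none to reproduce. Its only calculated size, 216 patients, reproduces: (1.960 + 0.842)² × 2 × 0.70 × 0.30 / 0.175² = 107.6, so 108 per arm. The present point does not depend on it, except that 108 is used below as the arm size.

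**Contacts after Day 1, through Week 24** (Sections 3.1 and 5.5.2.1)

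| Arm | Weeks | Count |
|---|---|---|
| 3.6 mg | 4, 8, 12, 16, 20, 24 | 6 |
| 10.8 mg | 12, 24 | 2 |

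The ratio is 6/2 = 3.0, or 7/3 = 2.3 with Day 1 counted. If 20 of the 108 patients on 10.8 mg are in the PK subgroup, each with three extra contacts, the mean is (88 × 2 + 20 × 5)/108 = 276/108 = 2.56 and the ratio is 6/2.56 = 2.3. Counting only visits that Section 3.1 schedules for safety, the ratio is 2/2 = 1.0.

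**Collection windows** (Section 6.4.3). For completers, Week 20 + 4 and Week 12 + 12 both give Week 24, so the windows coincide. They can differ for patients who stop early. For example, if the last dose is at Week 12 in both arms, collection runs to Week 16 on 3.6 mg and to Week 24 on 10.8 mg.

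**Possible size.** The following assumptions are not from the documents:
- True incidence is 40% in both arms, with one event per affected patient.
- Onset is uniform between contacts.
- Recall is lost exponentially with half-life h weeks.
- AEs are captured at every contact, and the PK visits are ignored.

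The fraction captured with a contact interval of T weeks is (1 − exp(−λT))/(λT), where λ = ln 2/h.

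| h (weeks) | Captured, T = 4 | Captured, T = 12 | Seen on 3.6 mg | Seen on 10.8 mg | Difference (points) |
|---|---|---|---|---|---|
| 4 | 0.721 | 0.421 | 28.9% | 16.8% | −12.0 |
| 12 | 0.893 | 0.721 | 35.7% | 28.9% | −6.9 |
| 52 | 0.974 | 0.924 | 39.0% | 37.0% | −2.0 |

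Differences are taken before rounding. With full recall both fractions are 1 and the difference is 0. It is also 0 if AEs are captured only at Weeks 12 and 24 in both arms.

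**The case against.** A reader might infer that AEs are elicited three times as often on 3.6 mg and that the comparison is therefore biased. The protocol does not support that. Section 3.1 schedules the same safety visits in both arms. Section 5.5.2.1 describes Weeks 4, 8, 16 and 20 as dosing occasions, and no text available says that the open question is asked then. Table 2 would normally settle this, but it is missing from that text. Three to one is a count of contacts, not a rate of questioning.

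Other counterarguments also have force:
- The open question covers the whole interval since the last asking, so nothing is excluded by design.
- AEs of oestrogen suppression, which Section 1.4 names as the most frequent, may persist and still be present at Week 12. The protocol does not call them short-lived.
- The longer window for some early stoppers on 10.8 mg pushes the other way.
- The AE comparison is descriptive, so no test or error rate is affected.
- Unequal contact is inherent in comparing 12-weekly with 4-weekly dosing.

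These points rule out a claim of established bias of known size, but they do not remove the risk. Even if the question is put only at Weeks 12 and 24, volunteered and observed events at the four extra 3.6 mg contacts still have to be recorded. The window offset does not apply to completers. Two of the three extra PK contacts fall on Days 2 and 3 and do little to shorten later recall. A descriptive estimate can still be shifted, and later analysis cannot recover events never recorded.

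**Conclusion.** The concern holds as a risk of unequal ascertainment. Planned post-dose contacts are 6 against 2, or against about 2.6 on average if 20 of 108 patients on 10.8 mg are in the PK subgroup. AE recording is not limited to the visits the arms share. Mild, transient AEs are liable to be under-recorded on 10.8 mg, and under-recording of this kind would favour that arm in the all-AE incidence.

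The documents do not fix the size. The range of 2 to 12 points rests wholly on the assumed 40% incidence and recall half-lives of 52 to 4 weeks, and zero remains possible. SAEs, severe events and persistent events should be little affected. The primary analysis and the sample size are untouched.

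**What to change.** In Section 12.2.2.1, keep the all-AE incidence and add by-arm summaries that depend less on contact frequency:
- SAEs, and AEs leading to discontinuation, both at present only listed by patient;
- AEs of CTCAE grade 3 or higher, which collapses the worst-grade table already planned;
- AEs ongoing at the common Week 12 and Week 24 visits, derived from recorded start and stop dates.

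State in the same section that differences in all-AE incidence must be read in light of the unequal contact schedules.

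The cost is a few extra tables from data that Section 6.4.3 already collects. The table of ongoing AEs does not capture events that resolve between visits, so it belongs beside the all-AE incidence and cannot replace it. Telephone AE contacts for 10.8 mg patients at Weeks 4, 8, 16 and 20 would bring the schedules closer at some cost in site time. They are optional, and the fix does not need them.
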